# 9 SUBJECT DISCONTINUATION AND STUDY OR SITE TERMINATION

# 9.1 Subject Discontinuation

Subjects will be encouraged to complete the study; however, they may voluntarily withdraw at any time. The Investigator will provide a report in the CRF describing the reason for discontinuation. If a subject withdraws before completion, every effort should be made to complete the assessments scheduled during the final scheduled assessment.

A subject may be terminated early from the study for the following reasons:

- The subject elects to withdraw consent from all future study activities, including follow-up.
- The subject is "lost to follow-up" (i.e., no further follow-up is possible because attempts to reestablish contact with the participant have failed).
- The subject dies.
- The subject develops a medical condition or is started on new medication(s) prohibited by the study or not previously mentioned in the list of prohibited medications that, in the opinion of the investigator, may pose additional risks from participation in the study, may interfere with the subject's ability to comply with study requirements or that may impact the quality of the data obtained from the study.
- If, in the course of an asthma exacerbation, a study investigator decides to discontinue study medication (ifetroban/placebo), the subject will be withdrawn from the study.
- In addition, subjects must be withdrawn from the study if any of the following occur:
  - Any serious adverse event related to study medication (ifetroban/placebo or aspirin) or to a study procedure
  - Serious arrhythmia requiring therapy
  - $\circ$  Thrombocytopenia  $< 50 \times 10^9/L$
  - Anemia (a fall in baseline hemoglobin of 10% or more)
  - Gastrointestinal bleeding

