 - CFB ACQ = post-treatment measurement – baseline
 - Any improvement in ACQ-7 (Yes or No): If CFB ACQ<0, then improvement =’Yes’; otherwise improvement = ‘No’
- Total Nasal Symptom Score (TNSS) AM and PM measurements
 - TNSS Daily Score = sum of the 4 symptom scores (congestion, runny_nose, nasal_itching, sneezing) for both AM and PM, separately. (listed only)
 - TNSS Visit Score: The daily score for AM and PM are averaged over time between the visits separately. Baseline Visit Score for AM and PM is obtained by averaging over the screening period and the day of the baseline visit. Week 4 Visit Score is obtained by averaging over the day after the baseline visit to the day of the Week 4 visit. Week 8 Visit Score is obtained by averaging over the day after Week 4 visit to the day of the Week 8 visit. Week 10 Visit Score is obtained by averaging over the day after Week 8 visit to the day of Week 10 visit.
 - CFB TNSS Visit Score = post-treatment measurement – baseline
- Frequency and Severity of Asthma Exacerbations (Respiratory Reaction Questionnaire)
 - Subject Frequency =count the number of reports since the previous visit for each visit
 - CFB Frequency = post-treatment measurement – baseline
 - Max Severity= define the maximum severity for each subject (none, mild, moderate, or severe) over the period since the previous visit.
 - Inhaler or rescue med (number of reports) count= count the number of reports where resp_rxn_inhaler >0 OR resp_rxn_add_tx_yn=Yes
 - CFB Inhaler or rescue= post-treatment measurement – baseline

- Frequency and Severity of Chronic Sinusitis (Sinus Infection Questionnaire)
 - Antibiotic use Frequency (number of reports) count= count the number of reports over the period since the previous visit where sinus_inf_antibio=yes
 - CFB Antibiotic use= post-treatment measurement – baseline

Pharmacodynamic Variables and biomarkers

- Plasma - Data from third party vendor
 - ScD10L (pg/mL)
 - Sp_selection (ng/mL)
- Biomarkers - Data from third party vendor.
 - Urine LTE4 (ng/mg Creatinine)
 - Urine PGD-M (ng/mg Creatinine)
 - Urine TX-M (ng/mg Creatinine)
 - Plasma F2 Isoprostanes (ng/mL)
 - Serum LTB4 (ng/mL)
 - SAM-Eicosanoids PGD2 (ng/mL)
 - SAM-Eicosanoids PXA2 (ng/mL)
 - SAM-Eicosanoids F2 Isoprostanes (ng/mL)

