5.1 Handling of Dropouts or Missing Data

Missing efficacy data which are not retrievable through queries will be imputed.

NRI

Binary response efficacy variables will be imputed by treating the missing data as a failure, ie, non-responder imputation (NRI). A response variable that is calculated from a continuous variable will only be imputed using NRI, not from the imputed continuous variable.

LOCF

Missing data for continuous efficacy variables with at least one post-baseline measurement will be imputed using Last Observation Carried Forward (LOCF). Any calculated continuous variable will be imputed after its creation.

If the baseline value is missing for any variable, then the last screening value will be used.

MI

Multiple imputation (MI) will be provided as a sensitivity analysis for the primary efficacy variable (SNOT-22 Score CFB) only. Six imputations will be calculated from PROC MI. Week 8 will be imputed using week 0 and week 4 by treatment by treatment. The analysis will be performed on the 6 imputed sets which will provide 6 estimates of LS means from separate analyses of ANCOVAs (see Section 7.1).

```
proc mi data=thedata out=outds n impute=6 seed=310
min=(-110 -110 -110 -110 -110 -110)
max=(110 110 110 110 110 110)
round=(1 1 1 1 1 1)
minmaxiter=100
noprint;
by trt;
var SNOT22BASE SNOT22CFB4 SNOT22CFB8;
run;
```

where SNOT22BASE is the baseline SNOT22 score and, SNOT22CFB4 and SNOT22CFB8 are the SNOT-22 Score values at Weeks 4 and 8, respectively.

The seed specified above will be used for development, but may be changed prior to unblinding; any such change will be documented. If convergence is not achieved with minmaxiter=100, then increase the number of iterations to 500. The properties of this approach, including convergence and collinearity, will be assessed prior to unblinding and may be adjusted to improve the operating characteristics.

After calculating the LS means of the two treatments and the estimated treatment difference and associated standard error from the ANCOVA, the 6 estimates can be placed in PROC MI analyze.

Code to obtain a single estimate of the treatment LS means and standard error.

```
proc mianalyze=thedata ; **Data output from proc mixed;  
by trt;  
modeleffects estimate; ***estimate of lsmeans for 6 sets;  
stderr stderr; *** estimate of standard error for 6 sets;  
run;
```

Code to obtain a single estimate p-value for the treatment difference.

```

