7.2 Secondary Efficacy Analyses

The analyses performed for the secondary efficacy variables will be combinations of summary statistics and ANCOVAs, using the normal approximation to the binomial (see Appendix A for details.) as appropriate, at specified visits presented in the table below.

The ANCOVA will include the corresponding value at Baseline as the only covariate with treatment. The LS means, standard error and p-values will be presented with corresponding the summary statistics.

Categorical variables will be analyzed using the normal approximation to the binomial distribution, assuming unequal variances. The p-value will be presented along with summary statistics.

The chart below outlines the analyses to be performed on each variable. It identifies the weeks in which the analysis will be performed for the variable of interest, the population, and the type of imputation.

Variable Name	Value Type	Pop	Weeks for Analysis			Imputation (2)
			Summary	ANCOVA	Binomial (1)	
SNOT-22	Score PCFB	ITT	0,4,8,10			LOCF
	Improvement(y/n)	ITT	0,4,8,10		4,8,10	NRI
SNOT-22 Subscale	Nasal Related	ITT	0,4,8,10			LOCF
	Ear and Facial	ITT	0,4,8,10			LOCF
	Quality of Life	ITT	0,4,8,10			LOCF
	Psychological	ITT	0,4,8,10			LOCF
	CFB Nasal Related	ITT	0,4,8,10			LOCF
	CFB Ear and Facial	ITT	0,4,8,10	4,8,10		LOCF
	CFB Quality of Life	ITT	0,4,8,10	4,8,10		LOCF
	CFB Psychological	ITT	0,4,8,10	4,8,10		LOCF
	22 Questions	ITT	0,4,8,10			LOCF
FEV1	Value	ITT	0,4,8,10			LOCF
	CFB	ITT	0,4,8,10	4,8,10		LOCF
PNIFR	Value	ITT	0,4,8,10			LOCF
	CFB	ITT	0,4,8,10	4,8,10		LOCF
UPSIT	Value	ITT	0,4,8,10			LOCF
	CFB	ITT	0,4,8,10	4,8,10		LOCF
FeNO	Value	ITT	0,4,8,10			LOCF
	CFB	ITT	0,4,8,10	4,8,10		LOCF
ACQ	Value	ITT	0,4,8,10			LOCF
	CFB	ITT	0,4,8,10	4,8,10		LOCF
	Improvement (y/n)	ITT	0,4,8,10		4,8,10	NRI

(1) Normal approximation to the Binomial
 (2) Imputation analysis outlined in Section 5.1. NRI=Non responder imputation, LOCF=Last observation carried forward

Variable Name	Value Type	Pop	Analysis			
			Summary	ANCOVA	Binomial (1)	Imputation (2)
TNSS AM/PM	Visit Score	ITT	4,8,10			LOCF
	CFB Visit score	ITT	4,8,10	4,8,10		LOCF
Asthma	Reports	ITT	0,4,8,10			LOCF
	CFB Reports	ITT	0,4,8,10	4,8,10		LOCF
	Max Severity	ITT	0,4,8,10			LOCF
	Rescue report	ITT	0,4,8,10			LOCF
	CFB rescue report	ITT	0,4,8,10	4,8,10		LOCF
Sinusitis	Reports	ITT	0,4,8,10			LOCF
	CFB Reports	ITT	0,4,8,10	4,8,10		LOCF
	Max Severity	ITT	0,4,8,10			LOCF
	Antibiotic report	ITT	0,4,8,10	4,8,10		LOCF

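### The SAP carries between-visit event counts forward after withdrawal, so a past interval's events or zero can be entered for a later interval the subject never entered

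*SAP*

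**What the plan says.** **The variable.** SAP 4.6 defines the asthma exacerbation count as an interval count: "Subject Frequency =count the number of reports since the previous visit for each visit". Antibiotic reports and Max Severity are also defined over the period since the last visit. The rescue count is a number of reports with no period stated. Sinusitis reports have no counting rule of their own.

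**The imputation.** SAP 5.1: "Missing data for continuous efficacy variables with at least one post-baseline measurement will be imputed using Last Observation Carried Forward (LOCF". It adds: "Any calculated continuous variable will be imputed after its creation". So the derived interval count, or its change from baseline, is what is carried.

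**The assignment.** SAP 7.2 says of its chart: "It identifies the weeks in which the analysis will be performed for the variable of interest, the population, and the type of imputation". The chart gives LOCF for every Asthma and Sinusitis row: reports, change in reports, Max Severity, rescue reports and antibiotic reports. It gives ANCOVA at Weeks 4, 8 and 10 for change in asthma reports, change in rescue reports, change in sinusitis reports, and antibiotic reports. Max Severity is summarised only.

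**The route to missing data.** Protocol 9.1 covers the case where "in the course of an asthma exacerbation, a study investigator decides to discontinue study medication (ifetroban/placebo), the subject will be withdrawn" from the study. Protocol 8.1 asks for the End of Treatment assessments after premature discontinuation of treatment, and Protocol 8.1.2 places that visit at Week 8. Protocol 9.1 asks instead for those of the final scheduled assessment. The SAP does not say which visit early-exit data belong to.

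**The concern.** Carrying a symptom score forward assumes that a state persists. Carrying an interval count forward asserts that the same number of new events occurred again in weeks when nobody observed the subject. A zero carried forward asserts, just as groundlessly, that no event occurred.

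The missingness need not be unrelated to the outcome. When the investigator stops study drug during an exacerbation, the subject leaves, and the last available count can be the one containing that exacerbation.

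At stake is a stated secondary objective: whether ifetroban reduces the frequency and severity of exacerbations and sinusitis, and the use of rescue medication and antibiotics. Nothing else in the SAP would expose the effect. Multiple imputation is confined to SNOT-22, and these counts have neither an exposure adjustment nor a sensitivity analysis.

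**Working it through.** **The plan's own figure.** The documents give no planning figure for the counts. The only one is the primary sample size (difference 12, SD 16, two-sided 0.05, 90% power):

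n = 2 × (1.960 + 1.282)² × (16/12)² = 37.4, so 38 per arm.

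Power at 38 per arm is 90.5% (normal approximation) or 89.7% (t-test). The figure reproduces and is not affected by this point. I use 38 below only as the arm size.

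**Step 1: how many intervals are copied.** Take a subject in the ITT Population with one exacerbation before Week 4 closes, who then leaves. Apply the SAP 4.6 definition and the SAP 5.1 rule:

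| Label given to the exit count | Week 4 | Week 8 | Week 10 | Intervals copied |
|---|---|---|---|---|
| Week 4 | 1 (real) | 1 (copied) | 1 (copied) | 2 |
| Week 8 | missing | 1 (real event, wrong interval) | 1 (copied) | 1 |
| Week 10 | missing | missing | 1 (real event, wrong interval) | 0 |

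Under the last two labels Week 4 cannot be filled, because there is no earlier post-baseline value. Protocol 8.1 points to the second row. The first row also describes a subject who attends Week 4 and then leaves with no later assessment. A subject with no SNOT-22 after baseline is outside the ITT Population (SAP 4.7), so nothing is copied.

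**Step 2: gross shift.** If k of 38 subjects in an arm each have one copied event at a visit, that arm's mean rises by k/38 compared with adding no event:

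- k = 1: 0.026
- k = 2: 0.053
- k = 4: 0.105

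**Step 3: shift against continuing subjects.** A subject who stayed might also have had events, so step 2 overstates the error. Let λ be the events per four weeks in those who continue. The documents give no value; I assume 0.1 to 0.5, and k from 1 to 4.

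- Week 8 excess = k(1 − λ)/38. Smallest: 1 × 0.5/38 = 0.013. Largest: 4 × 0.9/38 = 0.095.
- Week 10 excess = k(1 − λ/2)/38, because that interval is two weeks long. Smallest: 1 × 0.75/38 = 0.020. Largest: 4 × 0.95/38 = 0.100.

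**Step 4: carried zeros.** If k subjects leave with a count of zero, the Week 8 mean is understated by kλ/38. Smallest: 1 × 0.1/38 = 0.003. Largest: 4 × 0.5/38 = 0.053. At λ = 0.2, one carried event (+0.8/38) is cancelled by four carried zeros (4 × 0.2/38).

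**Step 5: Week 10.** Week 10 closes a two-week period off drug. A carried Week 4 or Week 8 count comes from an on-drug interval of up to about four weeks, so both the length and the treatment condition differ.

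**The case against.** A reader might infer that each early exacerbation with withdrawal is tabulated three times, so that any imbalance between arms is multiplied. The documents do not support this. The 1/1/1 pattern needs a Week 4 label or a Week 4 attendance; no text assigns early-exit data to Week 4, and Protocol 8.1 points to Week 8. No planned analysis adds the visits together either: a subject enters each visit's comparison once.

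A reader might also infer inflation in a known direction. That does not follow. Withdrawal under Protocol 9.1 depends on the investigator's decision to stop drug; an exacerbation alone does not trigger it. Zeros are carried too, and the balance of the two is unknown.

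Max Severity has no ANCOVA, so carrying it distorts summaries, not tests. It is also ordinal, whereas SAP 5.1 limits LOCF to continuous variables, so the chart and the rule disagree there.

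In the plan's defence, LOCF follows Protocol 11.5, the trial is a proof-of-concept Phase 2 study, the primary analysis is untouched, and recorded data are listed by subject and visit, so copied values could be traced.

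All of this limits the size and the direction. It does not answer the central point: the chart names these rows, the asthma definition is an interval count, and the carried values go into hypothesis tests.

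**Conclusion.** The point holds, and is limited to secondary endpoints. As written, the SAP can enter a past interval's count, whether an event or a zero, for a later interval the subject never entered, and then test it.

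For an event before Week 4 closes in an ITT subject, two later intervals are copied in the upper case, one under the label that Protocol 8.1 suggests, and none under a Week 10 label. Each copied event adds 0.026 to the arm mean at an affected visit compared with adding no event. Against the rate in continuing subjects, the Week 8 excess is 0.013 to 0.095. That range rests on assumed rates of 0.1 to 0.5 events per four weeks and 1 to 4 affected subjects of 38. Carried zeros pull the other way, so the net direction is not fixed. The change should be made, but the trial's main conclusion does not depend on it.

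**What to change.** In SAP 5.1 and the SAP 7.2 chart:

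- Remove LOCF from the asthma, rescue, sinusitis and antibiotic report rows, including their change-from-baseline rows, and from Max Severity.
- Count only events in observed time, including the interval that ends at the early-termination assessment.
- Compare arms with a count model, Poisson or negative binomial and chosen before unblinding, with the log of observed follow-up as offset.
- Summarise Max Severity and the Week 10 counts on observed data only.
- State the visit to which early-termination data are assigned, and reconcile the instructions in Protocol 8.1 and 9.1 with it.
- Record the departure from Protocol 11.5 in SAP section 9, which at present lists only the restriction of secondary analyses to the ITT Population.

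The cost is SAP wording, table footnotes and a little more programming, with no new data. The Week 10 summaries of these variables will include fewer subjects.

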# Pregnancy

Subjects who are prematurely terminated from the study will be followed to monitor safety for a minimum of 30 days or until resolution of the disqualifying event, whichever is longer, or until the Independent Safety Monitor, the CPI Director of Medical Affairs and the Principal Investigator determine that the follow-up is complete.

Subjects with early termination from this study will not be replaced.

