4.3 Randomization and Blinding

Subjects who meet all the inclusion and no exclusion criteria during the Screening/Baseline Period will be randomized using a 1:1 randomization ratio to receive either ifetroban 200 mg once daily or matching placebo. A central randomization will be utilized. Approximately 76 subjects shall be randomized to ensure at least 38 subjects per group will be analyzed for efficacy

The study will be double blind with respect to the treatment assignment. To maintain the study blind, the appearance of packaging and capsules will be identical in both study arms. Site and CPI clinical staff will be blinded to the treatment assignment until the completion of the study. Individual treatment assignment will remain blinded throughout the study. In the event a treatment assignment needs to be unblinded for safety reasons, the site principal investigator will notify the study project manager, who will consult with the medical monitor. The medical monitor will review the circumstances and grant approval as indicated. Any intentional or unintentional breaking of the blind will be reported to the Sponsor immediately and fully documented in the subject's case report form.

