4.5 Sample Size Determination

Thirty-eight subjects per group will provide 90% power for the comparison of ifetroban and placebo with respect to the change from baseline in SNOT-22 scores at Week 8 (two-sided, level 0.05), assuming a common standard deviation of 16 and a true difference is 12.

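### The multiple-imputation check on the LOCF primary analysis uses only six imputations and mis-specified code, so its p-value is noisy when the result is near 0.05

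*SAP*

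**What the plan says.** SAP section 7.1 makes the change from baseline in SNOT-22 at Week 8, ITT population with LOCF, the primary analysis. It repeats that analysis with MI to assess sensitivity. Section 5.1 gives the MI details:

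- Number of imputations: "Six imputations will be calculated from PROC MI". The seed is 310. It may be changed before unblinding if the change is documented.
- Imputation model, run by treatment arm: "var SNOT22BASE SNOT22CFB4 SNOT22CFB8", which is three variables.
- Limits: "min=(-110 -110 -110 -110 -110 -110", which is six values. The MAX list (110) and the ROUND list (1) also have six entries each.
- Definition: the sentence after the code describes `SNOT22CFB4` and `SNOT22CFB8` as SNOT-22 score values, although their names say change from baseline.
- Pooling: both MIANALYZE calls, as the text reads, attach the data set name directly to the procedure name without a data keyword.
- Review: the properties of the approach are to be assessed before unblinding and may be adjusted.

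Protocol section 6.3 gives the SNOT-22 range as 0 to 110. Protocol section 9.1 lists withdrawal rules and ends with: "Subjects with early termination from this study will not be replaced". Neither document states an expected dropout rate.

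**The concern.** MI estimates carry Monte Carlo error that shrinks only with the number of imputations, *m*. At *m* = 6 that error can be large enough to move a borderline p-value across 0.05 from one seed to the next. MI is the only specified check on the LOCF assumption, so a noisy answer weakens the one tool the plan has for showing whether the primary result depends on how missing Week 8 scores are filled in.

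The code raises a second problem. The length of the limit lists equals the number of imputations, not the number of variables, which suggests that the two were confused. With the name and the definition of the Week 4 and Week 8 variables in conflict, a programmer cannot tell from the text which quantity is to be imputed.

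**Working it through.** **1. The plan's own figure.** SAP section 4.5: "Thirty-eight subjects per group will provide 90% power", "assuming a common standard deviation of 16 and a true difference is 12", with a two-sided level of 0.05 and 1:1 allocation.

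- n per arm = 2 × (1.960 + 1.282)² × (16/12)² = 37.4, rounded up to 38.
- SE of the difference = 16 × √(2/38) = 3.67, and 12/3.67 = 3.27.
- Power = Φ(3.27 − 1.96) = 90.5% by the normal approximation, and 89.7% by the noncentral t.

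The stated 90% is reproduced, so 38 per arm and SD 16 were used below.

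**2. How *m* enters.** Let U be the mean within-imputation variance and B the between-imputation variance. Rubin's rules give T = U + (1 + 1/m)B, with degrees of freedom (m − 1)(1 + U/[(1 + 1/m)B])². The Monte Carlo SD of the pooled estimate is √(B/m). Going from 6 to 100 imputations divides it by √(100/6) = 4.1.

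**3. Simulation.** From the documents: 38 per arm, change SD 16, by-arm imputation from baseline and Week 4, rounding to 1, and ANCOVA on baseline and treatment. Assumed, because the documents do not say:

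- 2, 4 or 8 per arm missing Week 8 (5%, 11%, 21%), completely at random;
- baseline mean/SD of 45/18 or 35/12;
- correlation of Week 4 and Week 8 changes of 0.5 or 0.7;
- baseline–change correlation of −0.4.

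Each setting used 12 data sets and 400 seeds per *m*. The effect was shifted so that the p-value with very many imputations is 0.04. Share of seeds giving p > 0.05 (range over settings):

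| Missing per arm | m = 6 | m = 20 | m = 50 | m = 100 |
|---|---|---|---|---|
| 2 of 38 | 14–21% | 2–5% | 0.1–0.4% | 0% |
| 4 of 38 | 25–31% | 9–15% | 1–4% | 0.1–0.8% |
| 8 of 38 | 37–43% | 21–28% | 8–13% | 3–7% |

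A separate simulation with the same limiting p and missing counts gave 16%, 26% and 36% at *m* = 6, and 0%, 0% and 3.5% at *m* = 100.

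Central 95% range of the p-value over seeds, widest settings:

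| Missing per arm | m = 6 | m = 100 |
|---|---|---|
| 2 of 38 | 0.025–0.067 | 0.036–0.045 |
| 4 of 38 | 0.020–0.087 | 0.034–0.048 |
| 8 of 38 | 0.014–0.124 | 0.031–0.053 |

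**4. The limits, under each reading of the variables.**

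- *If they are scores*, a floor of −110 is wrong, because the scale starts at 0.
- *If they are changes*, −110 to 110 is the widest change that the scale allows, but a given patient's change can run only from −baseline to 110 − baseline. A patient at the minimum entry score of 20 could be given a total of 20 − 110 = −90 without breaching the limits.
- *Size of the second problem.* In the simulation about 2–7% of imputed Week 8 totals fell below 0. Imposing patient-specific limits moved the mean treatment difference by 0.04 to 0.28 points. Against the planned difference of 12, that is at most 0.28/12 = 2.3%.

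**The case against.** The best reply is that little turns on this. MI is a sensitivity analysis, and significance is decided on the LOCF result. The seed is stated and may change only before unblinding, with documentation, so the MI result is reproducible. SAP section 5.1 allows the method to be adjusted before unblinding, and SAP section 1 provides for review of the whole plan at that stage. The noise also matters only near the threshold. Take a Monte Carlo SD of 0.53 points, from a simulation with 6 per arm missing. Moving the planned difference of 12 by two such SDs (10.94 to 13.06) gives p of about 0.0007 to 0.004 with SE 3.67, or 0.003 to 0.011 with an assumed SE of 4.2. All of this stands. It limits the importance of the point, but it does not make six imputations precise. A fixed seed makes a noisy answer repeatable, not accurate, and permission to adjust the method does not set *m*.

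A reader might infer more than the documents support:

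- *That ±110 is an impossible range for a change score.* It is exactly the attainable range over all patients. The fault is that it is not tied to each patient's baseline.
- *That the limits cause the dependence on the seed.* They do not. The small *m* does, and any finite *m* does to some degree.
- *That the −110 floor would produce negative baselines.* Limits act only on imputed values. Section 5.1 replaces a missing baseline by the last screening value, and eligibility requires a screening score of at least 20, so baseline should not need imputing.
- *That MI would rest largely on impossible scores.* A mean baseline of 25, mean change of −20 and SD of 12 to 15 would put Φ(−5/12) to Φ(−5/15), or 34–37%, of totals below 0. That needs an 80% fall in the mean from near the entry floor. The broader assumptions above give 2–7%.
- *That the code will fail.* Whether it runs with six limits for three variables cannot be settled from the documents.

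**Conclusion.** The point holds as a low-severity correction to the sensitivity analysis. With six imputations and a limiting p of 0.04, roughly one seed in six (2 of 38 missing per arm) to two in five (8 of 38 missing) would put the MI p-value on the other side of 0.05. With 100 imputations the share is at most about 7%. These figures rest on assumed missingness, baseline and correlation values and on a result near the threshold; if the observed difference is close to the planned 12, the conclusion would not change.

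The mismatch in list length and the conflict between change and score are plain on the page. Their numerical effect on the treatment difference is small. The documents do not support saying that MI cannot show whether the primary result is robust, or that the primary result is affected.

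**What to change.** In SAP section 5.1, before unblinding:

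1. Use at least 100 imputations.
2. Impute the Week 4 and Week 8 SNOT-22 totals, then derive the change from baseline for the ANCOVA. This keeps every imputed total on the scale without patient-specific limits.
3. Give MIN, MAX and ROUND three entries each, in VAR order: 0, 110 and 1 for baseline, Week 4 and Week 8.
4. Rename the variables and correct their definition so that name, text and code agree.
5. Correct the data statement in both MIANALYZE calls.
6. Record the final seed before unblinding.

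The cost is a code edit and seconds of computing. No data collection changes, and the LOCF primary p-value stays as it is.
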